4.3 Testing Procedures

1. Visual acuity testing at all follow-up exams will be done without cycloplegia by a certified examiner using the ATS single-surround HOTV letter protocol on the Electronic Visual Acuity Tester.
 - Amblyopic eye visual acuity must also be retested with a -1.00D lens over the optimal refraction (to account for possible persistent accommodative tone).
 - If the sound eye visual acuity is reduced 1 or more lines from the previous visit, the sound eye must also be retested with a -1.00D lens over the optimal spectacle correction.
 - Follow-up visual acuity is considered the better of the two acuity measures (with and without the -1.00D lens). The protocol for conducting the visual acuity testing is described in the ATS Testing Procedures Manual.
 - For Visit B (18-week outcome exam) and all subsequent exams, if the better of the two visual acuities (with and without the -1.00D lens over spectacles) is not at least 1 line better than the visual acuity from the previous study visit, the study ends for this patient. If the better of the two visual acuities (with and without the -1.00D lens) is at least 1 line better than the visual acuity at the previous study visit, study follow-up continues.
2. Detection of strabismus at distance and near by cover/uncover testing, with measurement of any strabismus using the Simultaneous Prism and Cover Test (SPCT) and the Alternate Prism and Cover Test (APCT) (*section 2.3.2*) is performed through the optimal refractive correction. The SPCT should be performed before the APCT (*section 2.3.2*).
 - If the spectacles are bifocals, ocular alignment at near should be tested through the bifocal portion of the lenses. If necessary, the bifocals should be raised to ensure that the patient is viewing the near target in primary position (not down gaze) while looking through the bifocal lenses.
3. Stereoacuity with the Titmus Fly and Randot Preschool Stereoacuity tests

449 **4.4 Changes in Treatment Prior to the 18-week Outcome Visit**

- 450 • Amblyopia treatment in addition to spectacles (e.g., patching, atropine, vision therapy,
451 filters) is NOT allowed prior to the 18-week outcome exam.
- 452 • If the investigator determines that a spectacle change is required after the child has worn the
453 glasses initially prescribed, spectacles may be changed prior to the 18-week outcome exam.
454 Bifocals may be prescribed at any visit after the Baseline Visit if the esotropia at near
455 exceeds the esotropia at distance after wearing the single vision glasses.

456 **4.5 Follow-up Exams for Patients Still Improving**

457 Beginning at Visit B (18-week outcome exam) and for subsequent study visits, visual acuity in the
458 amblyopic eye will be classified as “stable” or “improving” based on the following criteria:

- 459 • Vision is considered “stable” when amblyopic eye visual acuity has not improved at least 1 line
460 (confirmed by a retest with a -1.00D lens over spectacles) from the previous study visit (Visit B
461 or subsequent 9-week Follow-up Exam).
- 462 • Vision is “improving” when amblyopic eye visual acuity has improved 1 or more lines from the
463 previous study visit.
- 464
- 465
- 466 ➤ If vision at Visit B (18-week outcome examination) or a subsequent 9-week Follow-up
467 Exam is classified as “stable,” the study is complete for this patient.
- 468 ➤ If vision is classified as “improving,” additional 9-week Follow-up Exams will be scheduled
469 every 9-weeks (± 10 days) until vision is classified as “stable.”

470

471 Testing at each 9-week Follow-up Exam will include the procedures listed in *section 4.3*. (visual
472 acuity, ocular alignment, and stereoacuity).

473 **4.6 Non-study Visits**

474 Non-study Visits may be scheduled at the discretion of the investigator between Visit B (18-week
475 outcome exam) and the first 9-week Follow-up Exam or between any two subsequent 9-week
476 Follow-up Exams. The investigator may discontinue the patient from the study if he or she feels
477 strongly that treatment in addition to spectacles is required.

478

479 Data from Non-study Visits will not be collected. Determination of visual acuity improvement is
480 made based on visual acuity measurements from Visit B (18-week outcome exam) and subsequent
481 9-week Follow-up Exams.

482 **4.7 Treatment Changes Following the 18-week Outcome Visit**

- 483
- 484
- 485 • If the investigator determines that a spectacle change is required, spectacles may be changed
486 following the 18-week outcome exam. Bifocals may be prescribed if the esotropia at near
487 exceeds the esotropia at distance after wearing the single vision glasses.
- 488 • Although discouraged, additional treatment may be started at any 9-week Follow-up exam
489 or Non-study Visit following the 18-week Outcome Visit if the investigator feels strongly
490 that treatment in addition to spectacles is required, even if the visual acuity has improved 1
491 line or more from the previous study visit. Starting any additional treatment will discontinue
492 the patient from the study.

493

CHAPTER 5: MISCELLANEOUS CONSIDERATIONS IN FOLLOW-UP

494
495
496
497
498
499
500
501
502
503
504
505
506
507
508
509
510
511
512
513
514
515
516
517
518
519
520
521
522
523
524
525
526
527
528
529
530
531
532
533
534
535
536
537
538
539
540
541

5.1 Maintaining Patient Follow-up

The Jaeb Center will maintain direct contact with the parents of each patient. Permission for such contacts will be included in the Informed Consent Form. The principal purpose of the contacts will be to develop and maintain rapport with the family and to help coordinate scheduling of the outcome examination. Additional contacts will be made if necessary for the scheduling of follow-up visits.

5.2 Patient Withdrawals

A patient (and in this case the parents) may withdraw from the study at any time. This is expected to be a very infrequent occurrence in view of the study design’s similarity to routine clinical practice. If the parents indicate that they want to withdraw their child from the study, the investigator should personally attempt to speak with them and determine the reason. If they do not want to change their child’s eye care provider, every effort should be made to comply with this and at the same time try to keep the patient in the study under the new provider’s care.

5.3 Management of Optical Correction

A refraction should be performed whenever the investigator suspects that refractive error may not be optimally corrected. If a spectacle change is needed, including the prescription of bifocal lenses, the cost of the lenses will be paid for by the study.

5.4 Management of Strabismus

Strabismus surgery is not allowed in the first 9 weeks of the study. Strabismus surgery is allowed at the investigator’s discretion following Visit A (9-week exam), although it is *strongly* preferred that surgery be delayed until after the 18-week outcome exam. Any surgeries performed during the study will be recorded in the comment section of the Follow-up Examination Form.

5.5 Risks of Examination Procedures

The procedures in this study are part of daily eye care practice in the United States and pose no known risks. As part of a routine usual-care exam, the patient may receive cycloplegic/dilating eye drops.

5.6 Reporting of Adverse Events

There is no adverse event reporting in this protocol. No procedures are being performed and no treatments are being prescribed that are not part of usual care. Investigators will abide by local IRB reporting requirements.

5.7 Discontinuation of Study

The study may be discontinued by the Steering Committee (with approval of the Data and Safety Monitoring Committee) prior to the preplanned completion of enrollment and follow-up for all patients.

5.8 Patient Payments

The parent of each patient will be compensated \$25 per visit for completion of the 9-week and 18-week visits. For patients remaining in follow up after the 18-week visit, \$25 will be paid for each 9-week Follow-up Exam, up to an additional \$100 (4 exams). The total maximum compensation for the study is \$150. If there are extenuating circumstances, additional funds may be provided for

542 travel if expenses exceed \$25 and the patient will be unable to complete the visit without the
543 reimbursement of the travel expenses.

544

545 **5.9 Benefits of Participation**

546 All patients will be given spectacles. Some patients will have an improvement in amblyopic eye
547 acuity and in some patients, amblyopia may resolve, obviating the need for additional treatment.

CHAPTER 6: SAMPLE SIZE ESTIMATION AND STATISTICAL ANALYSIS

548
549
550
551
552
553
554
555
556
557
558
559
560
561
562
563
564
565
566
567
568
569
570
571
572
573
574
575
576
577
578
579
580
581
582
583
584
585
586
587
588
589
590
591
592
593
594
595
596
597

The approach to sample size and statistical analyses are summarized below. A detailed statistical analysis plan will be written and finalized prior to the completion of the study. The analysis plan synopsis in this chapter contains the framework of the anticipated final analysis plan, which will supersede these sections when it is finalized.

6.1 Data Analysis

The study is evaluating 2 mechanisms by which strabismic amblyopia (with and without anisometropia) may be successfully treated by spectacle correction alone:

1. Correcting small amounts of blur (including small amounts of anisometropia), with a resultant focused foveal image, may be beneficial in strabismic and combined-mechanism amblyopia (even if the amblyopic eye is not fixing or when there is no reduction in the angle of deviation).
2. Correcting moderate amounts of hyperopia might reduce the magnitude of the strabismus, which may be beneficial to the amblyopic eye.

Patients will be classified into one of three groups based on the proposed mechanism of improvement:

1. Potentially improved because of the clear image hypothesis (amblyopic eye $\geq 1.00D$ astigmatism and/or $\geq 1.00D$ spherical equivalent anisometropia with no change in angle size at distance and near). A change in angle is defined as a reduction of 10Δ or more.
2. Potentially improved because of a reduced angle of strabismus (reduction of 10Δ or more at either distance or near)
3. Combination of improved image clarity and reduced angle size

Separate analyses will be conducted within these mechanistic subgroups. Patients dropped from the study before the 18-week outcome exam or who have had strabismus surgery before the 18-week outcome exam will not be included in the analysis.

For groups 2 and 3 above, an exploratory analysis will be performed based on change in strabismic angle size during the study. This will be defined as the change in magnitude from baseline to best alignment in order to categorize patients as:

- Change from heterotropia of $>10\Delta$ to a microtropia ($\leq 10\Delta$) or orthotropia at either distance or near
- Reduction of 10Δ or more at either distance or near
- Reduction of less than 10Δ or an increase in magnitude of deviation

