The ideal study design to answer the question of whether spectacles alone can significantly improve amblyopic eye visual acuity in strabismic children is a randomized trial with a control group who does not receive optical correction. However, most pediatric eye care providers would be reluctant to randomize esotropic children with hyperopic refractive error to a control

154 group of no optical correction because of the likelihood of some children having
155 accommodative esotropia, which would necessitate that hyperopic spectacles be prescribed.
156 The number of esotropic amblyopes without an accommodative component is sufficiently few
157 to make a randomized trial not feasible. Therefore, we have chosen to perform an observational
158 study with a large number of children with pure strabismic and combined-mechanism
159 amblyopia in order to evaluate the effect of refractive correction in this population of patients.
160

161 **1.2 Study Objective**

162 To evaluate the effectiveness of refractive correction alone for the treatment of previously
163 untreated strabismic or combined-mechanism amblyopia in children 3 to <7 years old.
164

165 **1.3 Synopsis of Study Design**

166 Major Eligibility Criteria (*see section 2.2 for a complete listing*)

- 167 • Age 3 to < 7 years
- 168 • Amblyopia associated with strabismus (with or without anisometropia)
- 169 • Visual acuity in the amblyopic eye between 20/40 and 20/400 inclusive through best
170 refractive correction
- 171 • Visual acuity in the sound eye 20/40 or better and inter-eye acuity difference ≥ 3
172 logMAR lines through best refractive correction
- 173 • Refractive error meeting at least 1 of the following criteria: $\geq 1.00D$ of astigmatism in
174 the amblyopic eye, $\geq 1.00D$ spherical equivalent anisometropia, or $\geq +2.00D$ spherical
175 equivalent hyperopia in either eye
- 176 • No prior amblyopia therapy
- 177 • No previous spectacle wear
- 178 • Investigator wishes to prescribe spectacles for refractive correction
179

180 Treatment

181 Patients will receive spectacles to correct their refractive error.
182

183 Visit Schedule

[figure not shown]
- 184 • Baseline exam
- 185 • Visit A: 9 weeks ± 10 days
- 186 • Visit B: 18 weeks ± 10 days (outcome exam by ATS certified examiner)
- 187 • 9-week Follow-up Exams: every 9 weeks ± 10 days (if needed- *section 4.5*) until amblyopia
188 resolves or until visual acuity does not improve at least 1 line (confirmed by a retest using a

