2.2 Eligibility and Exclusion Criteria

The following criteria must be met for the patient to be enrolled in the study:

1. Age 3-<7 years
2. Able to perform visual acuity testing using the ATS single-surround HOTV protocol
3. Amblyopia associated with strabismus (comitant or incomitant) with or without anisometropia
 - At least one of the following criteria must be met:
 - Heterotropia at distance and/or near fixation on examination (without spectacles)
 - History of strabismus surgery (or botulinum toxin extraocular muscle injection)
 - Documented history of strabismus that is no longer present (and which in the judgment of the investigator is the cause of amblyopia)
4. Visual acuity measured in each eye according to the procedures described in *section 2.3.2* that meet the following criteria:
 - Amblyopic eye 20/40 to 20/400 inclusive
 - Sound eye $\geq 20/40$
 - Inter-eye acuity difference ≥ 3 logMAR lines (i.e., amblyopic eye acuity at least 3 logMAR lines worse than sound eye acuity)
5. No previous spectacle correction
6. Refractive error meeting at least 1 of the following criteria: $\geq 1.00D$ of astigmatism in the amblyopic eye, $\geq 1.00D$ spherical equivalent anisometropia, or $\geq +2.00D$ spherical equivalent hyperopia in either eye.
7. Investigator wishes to prescribe spectacles to correct refractive error
8. No prior amblyopia treatment
9. No current vision therapy or orthoptics
10. No ocular cause for reduced visual acuity
 - Nystagmus per se does not exclude the patient if the above visual acuity criteria are met
11. Ocular examination within 2 months prior to enrollment
12. Cycloplegic refraction within 2 months prior to enrollment
13. No myopia ($\geq -0.25D$ spherical equivalent)
14. No prior intraocular or refractive surgery
15. No strabismus surgery planned in the 9 weeks following the Baseline Visit
16. Parent understands protocol and is willing to accept treatment
17. Parent has home phone (or access to phone) and is willing to be contacted by Jaeb Center staff
18. Relocation outside of area of an active ATS site within next 6 months not anticipated

251 **2.3 Screening Examination Procedures**

252 **2.3.1 Historical Information**

253 Historical information elicited will include the following: date of birth, gender, race, ethnicity, prior
254 amblyopia therapy (e.g., glasses, patching, pharmacologic, filters), and spectacle correction.

256 **2.3.2 Testing Procedures**

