6.1.1 Visual Acuity

Within each mechanistic subgroup, the proportion of patients with a 2 or more line improvement in amblyopic eye visual acuity will be calculated and an exact 95% confidence interval will be computed. A point estimate and 95% confidence interval for the mean lines of improvement in amblyopic eye visual acuity from baseline to 18 weeks will also be calculated. For each patient, the maximum acuity (at 18 weeks or after) and the visit at which this occurred will be determined. Analysis of acuity at this last visit will parallel the analysis done on visual acuity at 18-week outcome examination.

598 In the AT55 spectacle phase,⁷ the 23 patients with amblyopia cause defined as strabismus alone
 599 improved an average of 2.0 lines (SD = 1.5), with 74% improving 2 or more lines. The 42 patients
 600 with cause defined as combined-mechanism improved an average of 2.5 lines (SD = 2.0), with 64%
 601 improving 2 or more lines.

602
 603 **6.1.2 Factors Associated with Improvement in Visual Acuity**
 604 Exploratory analysis will evaluate whether patient factors such as magnitude of refractive error,
 605 baseline visual acuity, magnitude of anisometropia, stereoacuity, and change in magnitude of ocular
 606 deviation are associated with visual acuity improvement in the amblyopic eye.

607
 608 **6.1.3 Stereopsis and Ocular Alignment**
 609 To evaluate whether spectacle correction alone improves stereopsis and ocular alignment in patients
 610 not having surgery for strabismus, frequency distributions and cross-tabulations will be performed
 611 for the following:

- 612
- 613 • Stereoacuity as measured by the Randot Preschool Stereoacuity Test at the time of best
 614 amblyopic eye visual acuity compared with the stereoacuity at baseline with correction.
- 615 • Ocular alignment prior to spectacle wear compared with alignment after initial spectacle
 616 wear.
- 617 • Ocular alignment at the time of best amblyopic eye visual acuity compared with the
 618 alignment at baseline.

619
 620 **6.2 Sample Size**

621 Up to 150 patients will be enrolled. Recruitment may be discontinued if this goal is not reached
 622 within two years.

623
 624 Based upon recruitment data from AT55, it is estimated that 2 years of recruitment will result in the
 625 enrollment of 150 patients (about 6 per month) with amblyopia caused by strabismus (alone or with
 626 anisometropia), all of whom have had no prior treatment (including spectacles) for amblyopia.

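### The three mechanism groups leave out hyperopia-only children whose angle falls by less than 10Δ, and no whole-cohort acuity estimate is planned to answer objective 1.2

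*Protocol*

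**What the plan says.** The objective in section 1.2 is undivided: "To evaluate the effectiveness of refractive correction alone for the treatment of previously" untreated strabismic or combined-mechanism amblyopia at ages 3 to under 7 years.

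Section 2.2, item 6, lets a child in on any one of three refractive findings: astigmatism of at least 1.00D in the amblyopic eye, anisometropia of at least 1.00D, or at least +2.00D of "spherical equivalent hyperopia in either eye". Item 3 does not require a current deviation. One accepted route is "Documented history of strabismus that is no longer present", and no minimum angle is set.

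Section 6.1 then says "Patients will be classified into one of three groups based on the proposed mechanism of improvement":

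- Group 1 (clear image) needs astigmatism of 1.00D or more in the amblyopic eye and/or at least 1.00D of "spherical equivalent anisometropia with no change in angle size at distance and near". A change is defined as a fall of 10Δ or more.
- Group 2 (reduced angle) needs a fall of 10Δ or more at distance or near.
- Group 3 is the combination of the two.

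The same section adds "Separate analyses will be conducted within these mechanistic subgroups". Section 6.1.1 opens "Within each mechanistic subgroup, the proportion of patients with a 2 or more line improvement in amblyopic eye visual acuity will be calculated". The mean improvement follows in that paragraph, and the analysis of best acuity is to parallel both. The primary analysis in synopsis section 1.3 is set out the same way.

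**The concern.** The wording of section 6.1 presents the three groups as a complete classification. The only exclusions it names are children who leave the study, or have strabismus surgery, before the 18-week examination. If an eligible child can fit none of the groups, that child is lost from the main results without the protocol saying so.

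This matters for the question being asked. Section 1.1 argues that acuity gain from spectacles is not expected where the correction leaves the strabismus in place, and calls for a larger study to confirm or refute the earlier gains. Children without a 10Δ reduction, and without the blur factors listed for group 1, are a direct test of that argument. In addition, three separate subgroup estimates do not give one answer for the population named in 1.2. Nor would pooling the three groups give it, unless the children outside them respond alike.

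**Working it through.** **1. The plan's own figures.** Section 6.2 expects 150 × 0.90 = 135 patients for analysis. Subgroups of 25%, 50% and 75% are 33.75, 67.5 and 101.25, shown as 34, 68 and 102. The half-widths follow 1.96 × SD/√n and 1.96 × √(p(1−p)/n):

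- Mean, SD 1.5, n = 34: 1.96 × 1.5/√34 = 0.504 (stated 0.5).
- Proportion 0.40, n = 33.75: 1.96 × √(0.40 × 0.60/33.75) = 0.165 (stated 0.17).

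All 24 cells reproduce, the proportions with unrounded n. The precision arithmetic is sound. The tables have no column for the whole 135.

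**2. Coverage of the groups.** Three refractive criteria, at least one met, give 2³ − 1 = 7 combinations. Each is crossed with angle reduction of 10Δ or more (yes or no), giving 14.

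| Refraction | Reduction of 10Δ or more | Less than 10Δ |
|---|---|---|
| Astigmatism and/or anisometropia of 1.00D or more (6 combinations) | Group 3 | Group 1 |
| Hyperopia of +2.00D or more only (1 combination) | Group 2 | **No group** |

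Covered: 6 + 6 + 1 = 13. Not covered: 1. This reads group 2 as excluding children who meet group 3. As literally written, the six combinations in group 3 also satisfy group 2.

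**3. Children who are unclassifiable from entry.** Take the angle as the manifest deviation. A hyperopia-only child with no current tropia, or with less than 10Δ at both distance and near, cannot show a 10Δ fall. Section 2.2, item 3, admits such children.

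**4. Where acuity is estimated.** The proportion with 2 or more lines, the mean lines and the best-acuity analysis are all placed within the groups (1.3, 6.1, 6.1.1). The exploratory analyses in 6.1.2 and 6.1.3 are not confined to the groups. But 6.1.2 looks at factors associated with improvement, and 6.1.3 at stereopsis and alignment. Neither gives an overall acuity effect.

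**5. Size.** Let u be the share of analysed children in no group and d the response rate in the groups minus the rate outside them. The pooled three-group rate then differs from the whole-cohort rate by u × d. The protocol gives neither u nor d. For illustration only, assume 7 to 40 of 135 children unclassified (about 5% to 30%) and d = 18 percentage points in either direction:

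- 7/135 × 18 = 0.9 points
- 40/135 × 18 = 5.3 points

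The sign is that of d, which is unknown.

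**6. What a whole-cohort estimate would give at N = 135.**

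- Mean: 1.96 × 1.5/√135 = 0.25 lines and 1.96 × 2.0/√135 = 0.34 lines, using the earlier SDs quoted in 6.1.1.
- Proportion: at the earlier rates of 64% and 74% (86 and 100 of 135), exact (Clopper-Pearson) half-widths are 0.084 and 0.077.

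**The case against.** **The later plan may mend this.** The opening of chapter 6 calls the chapter a synopsis that a final analysis plan will supersede, and an overall row is often left to such a plan. It stands that the gap may have been closed there. But the incomplete classification is stated in the protocol, and the synopsis fixes the primary analysis inside it. That is more than a detail left open.

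**The study is about mechanisms.** Section 6.1 says it evaluates two mechanisms, so analysis by mechanism is a legitimate choice. That stands, and the groups should stay. It does not supply an estimate for objective 1.2.

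**Hyperopic blur could count as clear image.** The first mechanism in 6.1 speaks of correcting blur generally. But the operational definition of group 1 lists only astigmatism and anisometropia, and 6.1 ties hyperopia to the angle mechanism.

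Four stronger readings are tempting and not supported:

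- *The children are analysed nowhere.* Sections 6.1.2 and 6.1.3 are not limited to the groups, and 6.2 counts all expected completers.
- *The results are biased upward.* In the earlier data, strabismus alone reached 2 or more lines at least as often as combined mechanism (74% against 64% in 6.1.1; 75% against 69% in 1.1). Mean lines ran the other way (2.0 against 2.5; 2.2 against 2.6). Neither dataset is split by angle change.
- *The size can be read from the share with strabismus alone.* That share is 23/65 = 35% or 12/25 = 48%. The missing cell also requires astigmatism below 1.00D and a reduction under 10Δ, and the protocol gives no frequency for either.
- *The groups are post hoc.* They are prespecified, although they use the angle response to correction.

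**Conclusion.** The point holds. One of the 14 eligible combinations, hyperopia alone with less than a 10Δ reduction, has no group. Children in it enter no planned proportion, mean or best-acuity estimate, and objective 1.2 has no overall estimate. This rests only on the definitions in 2.2 and 6.1 as written, and on the placing of the acuity analyses in 1.3 and 6.1.1. The sentence on mean improvement does not itself repeat the subgroup condition, but its paragraph, section 6.1 and the synopsis all put it there.

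The number of children affected and the direction of any bias cannot be known from the protocol. The figures in step 5 are assumptions and not findings. In a single-arm estimation study that collects the same data on every child, this should be fixed before analysis. It does not undermine the data.

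A fourth group alone does not give each child one place. Section 6.1 does not say which visits or which of the two prism cover tests define the grouping angle. Its exploratory analysis of groups 2 and 3 runs from baseline to best alignment and includes a category for falls under 10Δ, which suggests that the grouping uses a different interval.

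**What to change.** 1. In 1.3 and 6.1.1, add a whole-cohort estimate at 18 weeks as the answer to objective 1.2: the proportion improving 2 or more lines with an exact 95% confidence interval, and the mean lines improved with a 95% confidence interval.
2. In 6.1, add a fourth group: neither astigmatism nor anisometropia of 1.00D or more, and no reduction of 10Δ or more.
3. In 6.1, state that group 2 excludes children who meet the definition of group 3.
4. In 6.1, state which two visits and which alignment test (simultaneous or alternate prism and cover) define the grouping angle change, so that every analysed patient falls in exactly one group.

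The cost is wording, one more table column and an overall row. No extra patients, visits or measurements are needed. The overall figure may be less favourable than the subgroup figures.

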4.1 Treatment

Each patient will receive spectacles with his/her optimal correction (*section 2.5*), paid for by the study. No additional treatment will be provided to patients in this study.

- If a patient receives active treatment (e.g., patching, atropine, filters, visual therapy) of any kind, the patient will end study follow-up.
- If glasses are worn prior to the baseline visit for more than one day, the patient will end study follow-up.

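### Excluding children who leave, start other amblyopia treatment or have surgery before 18 weeks makes the reported improvement likely, though not certain, to be overstated

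*Protocol*

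**What the plan says.** Section 6.1 fixes the analysis set with an explicit rule: "Patients dropped from the study before the 18-week outcome exam or who have had strabismus surgery before the 18-week outcome exam will not be" included.

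Section 4.1 determines who counts as dropped. "If a patient receives active treatment (e.g., patching, atropine, filters, visual therapy) of any kind, the patient will end study follow-up". The same section gives an exit unrelated to response: "If glasses are worn prior to the baseline visit for more than one day, the patient will end study follow-up".

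On surgery, section 5.4 states: "Strabismus surgery is not allowed in the first 9 weeks of the study". After Visit A it is left to the investigator, with a strong preference for waiting until after the 18-week exam. Surgery does not end follow-up. A child operated on between weeks 9 and 18 can therefore attend the outcome exam and still be left out of the acuity analysis.

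Section 6.1.3 introduces its comparisons with "To evaluate whether spectacle correction alone improves stereopsis and ocular alignment in patients" and then restricts them to children who have no strabismus surgery. It sets no time limit on that surgery.

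The protocol states no analysis that retains the excluded children or bounds their effect.

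**The concern.** The objective in section 1.2 is the effectiveness of refractive correction alone. A child who needs patching or atropine before week 18 says something about that effectiveness, yet leaves both numerator and denominator. Section 1.1 explains why there is no untreated control group, so no comparator shares and cancels the selection. The planned exact confidence interval covers sampling error only.

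The alignment question has a similar problem. Children whose eyes stay misaligned in spectacles are plausible candidates for surgery, so section 6.1.3 asks whether spectacles improve alignment in a group that may be favourably selected. One of its three comparisons sets alignment before spectacle wear against alignment after initial wear. On a natural reading that comparison is complete at the Baseline Visit, before any surgery is permitted, so later surgery gives no reason to discard it.

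The proportion gaining 2 or more lines and the mean gain are the study's results, so a shift in either changes its main message.

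**Working it through.** **Inputs from the protocol**
- Section 6.2: "Up to 150 patients will be enrolled"; 90% are assumed to complete; 135 are expected for analysis.
- Section 6.1.1, benchmarks from the earlier study's spectacle phase: strabismic, 74% gaining 2 or more lines, mean 2.0 lines; combined-mechanism, 64%, mean 2.5 lines.

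**Assumption.** The response rate q in excluded children is not in the protocol. I take it from 0% to 100%.

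**Step 1: the plan's own figure.** 150 × 0.90 = 135, which reproduces. It leaves 15 children out. The allowance is for non-completion only; nothing is added for completers removed because of surgery.

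**Step 2: rate with all children counted.** With p the rate in the 135 analysed, the overall rate is (135p + 15q)/150. The overstatement is p minus this, which equals 0.10 × (p − q).

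| q | p = 74% | p = 64% |
|---|---|---|
| 0% | 99.9/150 = 66.6% | 86.4/150 = 57.6% |
| 25% | 103.65/150 = 69.1% | 90.15/150 = 60.1% |
| 50% | 107.4/150 = 71.6% | 93.9/150 = 62.6% |
| q = p | 74% | 64% |
| 100% | 114.9/150 = 76.6% | 101.4/150 = 67.6% |

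The shift therefore runs from an overstatement of 7.4 or 6.4 points (q = 0) to an understatement of 2.6 or 3.6 points (q = 100%).

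**Step 3: whole-number counts with exact 95% intervals.**
- 100/135 = 74.1% (65.8 to 81.2); with 15 failures added, 100/150 = 66.7% (58.5 to 74.1).
- 86/135 = 63.7% (55.0 to 71.8); with 15 failures added, 86/150 = 57.3% (49.0 to 65.4).

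**Step 4: means.** If excluded children gained nothing, 2.0 × 0.90 = 1.8 lines and 2.5 × 0.90 = 2.25 lines, a drop of 0.2 to 0.25 lines.

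**Step 5: scale against precision.** At N = 135 the exact half-widths from step 3 are (81.2 − 65.8)/2 = 7.7 and (71.8 − 55.0)/2 = 8.4 points, so the worst-case shift is nearly as large. Results are to be reported by mechanistic subgroup, however. By normal approximation, 1.96 × √(0.74 × 0.26/n) gives 14.7, 10.4 and 8.5 points at n = 34, 68 and 102, all wider than the worst-case 7.4. Within a subgroup the overstatement is m × (p − q), with m that subgroup's own excluded share.

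**Step 6: if more than 10% are excluded.** Each further 5% of children excluded (an assumption) adds at most 0.05 × 74 = 3.7 or 0.05 × 64 = 3.2 points.

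**The case against.** The protocol limits these events. Section 4.4 says that added amblyopia treatment "is NOT allowed prior to the 18-week outcome exam", so a child treated early is a deviation and not a routine exit. Surgery planned within 9 weeks of baseline bars entry, and later surgery is preferably deferred. Section 5.2 expects withdrawal "to be a very infrequent occurrence in view of the study" design's closeness to ordinary care. All this stands and keeps the numbers small. But section 4.1 still provides the exit, and section 6.2 still plans for 10% loss.

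Setting aside acuity measured after surgery is also defensible. The question is spectacles alone, and surgery changes the angle on which the mechanistic groups are defined. That justifies not using post-surgery values; it does not justify discarding values recorded before surgery. Surgery is allowed only after Visit A, so operated children should have spectacle-corrected data at baseline and 9 weeks.

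Chapter 6 is a synopsis that a later analysis plan will supersede. Imputation details may properly wait for that plan. The exclusion is different: it is a stated rule in what the protocol calls the framework for the final plan.

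A reader might infer that the bias must run towards effectiveness. The documents do not show this. Some exits, such as spectacles worn early or family withdrawal, are not evident failures. For the period after 18 weeks, section 4.7 recognises that treatment may be added even when acuity has gained a line or more, so starting treatment does not amount to non-improvement. Nor is surgery in itself an acuity failure.

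**Conclusion.** The concern holds in a limited form. The analysis set is conditioned on post-baseline events plausibly tied to poor response or persistent misalignment, and no stated analysis shows the effect. Overstatement is likely but not established; it occurs only if excluded children respond less often than analysed ones.

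At 10% exclusion and the benchmark rates, the most it can reach is 7.4 or 6.4 points, or 0.2 to 0.25 lines if excluded children gained nothing. These are upper bounds for that level of loss. Enrolment precedes the Baseline Visit, and under section 3.4 some of the 15 may prove ineligible there and would not belong in the denominator. Others may leave for unrelated reasons. The 10% figure does not cover completers removed for surgery, so the excluded share itself could be larger; the protocol gives no figure for that.

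A reader might also take the rule to remove every operated child from the acuity result. It does not: only surgery before the 18-week exam does so. The unlimited restriction applies to alignment and stereopsis in section 6.1.3.

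Severity is moderate.

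**What to change.** In section 6.1, define the analysis set as all children who still meet eligibility at the Baseline Visit and received the spectacles. Within it:

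- **Other amblyopia treatment started before 18 weeks:** count as not improved by 2 or more lines. Add a sensitivity analysis using the last study acuity before that treatment, since a child may already have gained 2 lines at Visit A.
- **Surgery before 18 weeks:** use the last spectacle-corrected acuity and alignment before surgery, for the outcome and for mechanistic group assignment.
- **Other losses:** use Visit A data where they exist, and report best-case and worst-case bounds.
- **Present completer, non-surgical analysis:** keep it alongside, and tabulate exclusions by reason and by mechanistic group.

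In section 6.1.3, include operated children with their last pre-surgery alignment and stereoacuity.

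The cost is rewording two sections and modest programming, with no new visits, patients or change in care. Surgery is recorded in a comment field (section 5.4), so its date must be retrievable to order it against the visits; the present rule needs that too. The drawbacks are somewhat more analysis work and a headline rate that may be less favourable. Failure coding of treatment starters is a convention, which is why the sensitivity analysis should accompany it.
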